4.3 EXPLORATORY ENDPOINTS

5 SAMPLE SIZE CONSIDERATIONS

The sample size calculation is based on the following assumptions:

- The primary endpoint “change from baseline to Day 8 in SARS-CoV-2 viral shedding” is normally distributed
- One-sided significance level $\alpha = 5\%$
- True maximum treatment effect size of BGB-DXP593 versus placebo is $-1.5 \log_{10}$ copies per mL
- Standard deviation is $3.2 \log_{10}$ copies per mL (Wang et al 2020)
- Prespecified candidate models listed in Section 6.4.1

Forty-one patients are needed with primary endpoint data per arm to provide at least 82% power to detect non-flat dose-response relationship. MCPMod approach is used. In order to ensure 41 patients per arm with primary endpoint data, at least 43 patients per arm need to be randomized to account for potential dropout rate of 5%.

The calculation has been performed using R software, version 3.6.1.

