6 STATISTICAL METHODS

6.1 ANALYSIS SETS

- The Intent-to-Treat (ITT) Analysis Set includes all randomized patients. Patients will be analyzed according to the treatment assigned at randomization. This will be the primary analysis set for efficacy analyses.
- The Safety Analysis Set includes all patients who have received the study drug (BGB-DXP593 or placebo). Patients will be analyzed according to their actual treatment received. The Safety Analysis Set will be used for all safety analyses.
- The PK Analysis Set includes all patients who received the study drug (BGB-DXP593) per the protocol and for whom any postdose PK data are available.
- The ADA Analysis Set includes all the patients who received the study drug and in whom both baseline ADA and at least 1 postbaseline ADA results are available.

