6.2 DATA ANALYSIS GENERAL CONSIDERATIONS

6.2.1 Definitions and Computations

Study day is calculated in reference to the date of randomization. For assessments conducted on or after the date of randomization, study day will be calculated as assessment date – date of randomization + 1. For assessments conducted before the date of randomization, study day is calculated as assessment date – date of randomization. There is no study day 0.

In the situation where the event date is partial or missing, the date will appear partial or missing in the listings. Study day and any corresponding durations will be presented based on the imputations specified in Appendix 10.1.

Baseline is defined as the last non-missing value collected before the administration of the study drug.

All calculations and analyses will be conducted using SAS version 9.4 or higher.

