6.2.4 Multiplicity Adjustment

The MCPMod procedure allows for simultaneous evaluation of different potential dose response patterns, whilst protecting the overall probability of Type I error (one-sided α of 5%). No additional multiplicity adjustments will be made in this study. Two-sided 90% confidence interval will be used to describe the precision of the rate estimate whenever appropriate.

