6.4.2 Secondary Endpoint Analyses

Secondary efficacy endpoints will include:

- Time-weighted average change in viral shedding as measured by RT-qPCR in nasopharyngeal swab samples from baseline to Day 15
- Change in SARS-CoV-2 viral shedding as measured by RT-qPCR in nasopharyngeal swab samples from baseline to Day 15
- Time to negative RT-qPCR in all tested samples with no subsequent positive RT-qPCR in any tested samples
- Proportion of patients requiring hospitalization due to worsened COVID-19
- Time to resolution of all COVID-19-related symptoms
- All-cause mortality rate at Day 29

The time-weighted average change in viral shedding as measured by RT-qPCR in nasopharyngeal swab samples from baseline to Day 15 is defined as:

$$\frac{\sum_{i=a}^{b-1} [0.5 \times (Y_i + Y_{i+1}) \times (t_{i+1} - t_i)]}{t_b - t_a}$$

where Y_i is the change from baseline in viral shedding at Visit i , t is the time at the specified timepoint (the actual study day), a is the baseline assessment at Day 1, and b is the last assessment at or prior to Day 15 visit. Analysis of covariance (ANCOVA) model with corresponding baseline viral shedding, disease severity at baseline, and treatment as covariates will be used. Comparisons of active doses to placebo (90% CIs and p-values) will be provided.

The same MMRM analysis for primary endpoint will be used to analyze the change in SARS-CoV-2 viral shedding from baseline to Day 3 and Day 15. Comparisons of active doses to placebo (90% CIs and p-values) will be provided.

[figure not shown]
The negative RT-qPCR is defined as the value that is below the lower limit of detection. Kaplan-Meier method will be used to assess the time to negative RT-qPCR. The corresponding quartiles (including the median) will be reported and a two-sided 90% CI of median, if estimable, will be constructed with a generalized Brookmeyer and Crowley method for each dosing group. Patients who have died prior to experiencing the event of interest will be censored on the day of data cutoff. Patients for whom the RT-qPCR value is still positive by the time of end of study visit or data cutoff, whichever comes first, will be censored on the last RT-qPCR sample date.

[figure not shown]
The number of patients who require hospitalization due to worsened COVID-19 will be counted. Corresponding proportion will be derived and a two-sided binomial exact 90% CI of proportion will be constructed.

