Time to resolution of all COVID-19-related symptoms is defined as the days from randomization to the first day when all symptoms were resolved. Kaplan-Meier method will be used to assess the time to resolution of all COVID-19 related symptoms. The corresponding quartiles (including the median) will be reported and a two-sided 90% CI of median, if estimable, will be constructed with a generalized Brookmeyer and Crowley method for each dosing group. Patients who have died prior to experiencing the event of interest will be censored. Their follow-up length will be arbitrarily set as (data cutoff date – first patient in date). This approach is to count death as the worst possible outcome without possibility of recovery. Patients who have ongoing symptoms will be censored at the time of end of study visit or data cutoff, whichever comes first.

[figure not shown]
Kaplan-Meier method will be used to assess all-cause mortality rate at Day 29. A two-sided 90% CI of this rate, if estimable, will be constructed using the Greenwood's formula. Patients who do not die will be censored at the time of end of study visit or data cutoff, whichever comes first .

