6.5.2 Adverse Events

The AE verbatim descriptions (investigator's description from the eCRF) will be coded using MedDRA. AEs will be coded to MedDRA lowest level term, preferred term, and primary system organ class.

A TEAE is defined as an AE that had an onset date or a worsening in severity from baseline (pretreatment) on or after the administration of study drug and up to the 30 days after dosing.

The incidence of TEAEs will be reported as the number (percentage) of patients with TEAEs by system organ class and preferred term. A patient will be counted only once by the highest severity grade per NCI-CTCAE Version 5.0 within a system organ class and preferred term, even if the patient experienced more than 1 TEAE within a specific system organ class and preferred term. The number (percentage) of patients with TEAEs will also be summarized by relationship to the study drug.

Treatment-related TEAEs include those events considered by the investigator to be related to study treatment or with missing assessment of the causal relationship. SAEs, deaths, \geq Grade 3 TEAEs, treatment-related TEAEs, and TEAEs that led to treatment discontinuation or treatment interruption will be summarized.

An overview table of patients with at least one TEAE will be presented with the incidence of:

- patients with any TEAE
- patients with any TEAE with grade 3 or higher
- patients with any serious TEAE
- patients with any TEAE leading to death
- patients with any TEAE leading to treatment discontinuation
- patients with any TEAE leading to drug interruption
- patients with any TEAE leading to infusion rate decreased

- patients with any treatment-related TEAE
- patients with any treatment-related TEAE with grade 3 or higher
- patients with any treatment-related serious TEAEs

-
- patients with any treatment-related TEAE leading to death
 - patients with any treatment-related TEAE leading to treatment discontinuation
 - patients with any treatment-related TEAE leading to drug interruption
 - patients with any treatment-related TEAE leading to infusion rate decreased

Treatment-related AEs also include those events with missing assessment of the causal relationship.

The incidence of following TEAEs will be reported by SOC and PT, sorted by decreasing order of the frequency of the SOC first and then by decreasing order of the frequency of the PT within the SOC:

- patients with any TEAE
- patients with any serious TEAE
- patients with any TEAE leading to death

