6.8 OTHER EXPLORATORY ANALYSES

7 INTERIM ANALYSIS

A primary analysis of efficacy and safety is planned after all patients have finished Day 8 visit or discontinued the study earlier. Pharmacokinetic, immunogenicity and exploratory biomarkers will not be a part of the primary analysis.

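### For an arm with no deaths, the planned Greenwood interval for Day 29 mortality is 0% to 0% or missing, although 0 of 43 is compatible with mortality up to 6.7%.

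*SAP*

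**What the plan says.** - **Mortality interval (SAP 6.4.2).** All-cause mortality at Day 29 is estimated by Kaplan-Meier. On its uncertainty, the SAP says "A two-sided 90% CI of this rate, if estimable, will be constructed using the" Greenwood formula. It does not say when an interval counts as estimable, whether the limits are untransformed or log-log, or what is shown if nobody in an arm dies.
- **Protocol 10.2.2.** This gives no fallback either. It plans Kaplan-Meier quartiles and a 95% interval for the median survival time, with no interval for the Day 29 rate.
- **Purpose of the intervals (SAP 6.2.4).** "Two-sided 90% confidence interval will be used to describe the precision of the rate estimate whenever appropriate".
- **Hospitalisation (SAP 6.4.2).** For this other infrequent outcome, "a two-sided binomial exact 90% CI of proportion will be constructed".
- **Analysis set (SAP 6.1).** Of the ITT set: "This will be the primary analysis set for efficacy analyses".
- **Arm size (SAP 5).** At least 43 patients per arm "need to be randomized to account for potential dropout rate of 5"%, to leave 41 with primary endpoint data.

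**The concern.** Greenwood's variance is a sum over death times. With no deaths there is nothing to sum and the variance is zero, whatever the sample size. The reported interval then either claims perfect knowledge of the mortality rate or is left out. Neither meets the purpose the SAP sets for its 90% intervals.

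The trial enrols mild to moderate disease, excludes severe COVID-19 (Protocol 4.2) and has about 43 patients per arm, so an arm without deaths is a realistic outcome. At stake is the uncertainty statement for a named secondary endpoint. Without a rule, the choice of interval may be made after the death counts are known.

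**Working it through.** **Inputs.** 43 randomized per arm, 41 after dropout (SAP 5); two-sided 90% level, so z = 1.645 (SAP 6.4.2). The arm size is consistent with the stated dropout: 41/0.95 = 43.2 and 43 × 0.95 = 40.9. The documents state no figure for the mortality interval and no mortality rate for this population, so the rates below are assumed. All calculations take every patient as followed to Day 29.

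**Step 1: Greenwood with no deaths.** SE = S × √Σ[d/(n(n − d))]. With d = 0 throughout, S = 1 and SE = 0.
- Untransformed: 0 ± 1.645 × 0, which is 0% to 0%.
- Log-log: needs log(−log 1) = log 0, which is undefined.

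**Step 2: exact limit with no deaths.** The upper Clopper-Pearson 90% limit is 1 − 0.05^(1/n).
- 0 of 43: 1 − 0.05^(1/43) = 6.73%.
- 0 of 41: 1 − 0.05^(1/41) = 7.05%.

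**Step 3: one death in 43.** The estimate is 2.3%, with SE 2.30 points.
- Untransformed Greenwood: −1.5% to 6.1%.
- Log-log: 0.5% to 11.5%.
- Exact: 0.1% to 10.6%.

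The untransformed form therefore gives an impossible lower limit even when there is a death.

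**Step 4: how often it arises, and coverage.** P(no deaths in an arm) = (1 − p)^43, and P(at least one of four arms has none) = 1 − [1 − (1 − p)^43]^4. Coverage is by binomial enumeration at n = 43, counting a 0% to 0% interval as a miss.

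| Assumed Day 29 mortality | No deaths in a given arm | At least one such arm of four | Untransformed Greenwood coverage | Exact coverage |
|---|---|---|---|---|
| 0.5% | 81% | 99.9% | 19% | 98% |
| 1% | 65% | 98% | 35% | 99% |
| 2% | 42% | 89% | 57% | 99% |
| 4.6% | 13% | 43% | 85% | 95% |

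The 4.6% row is the crude ratio 550,000/12,000,000 from Protocol 1.4. It covers all severities worldwide and serves only as a high reference point.

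**Step 5: where the loss comes from.** Among arms with at least one death, untransformed Greenwood covers 99.3%, 99.7%, 98.2% and 98.5% at the four rates. Almost all of the shortfall comes from zero-death arms.

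**Step 6: candidate replacements**, over mortality from 0.05% to 6% in steps of 0.01 points.
- Exact in every arm: coverage 95.0% to 99.9%.
- Log-log where there are deaths, exact where there are none: minimum 82.4% at 0.45% mortality. It is below 90% at 0.25–0.45%, 1.25–1.47%, 2.60–2.75% and 4.12–4.19%.

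**The case against.** The strongest reply is that the estimability condition already deals with this. A zero variance is not usable, so the natural reading is that no interval is shown for a zero-death arm. SAP 6.2.4 likewise asks for intervals only where appropriate. On that reading the defect is a missing interval, and the 19%, 35% and 57% coverages do not arise. The last part stands: those figures apply only if 0% to 0% is printed. But the condition is undefined, a zero standard error can be computed, and omission still leaves the endpoint with no statement of uncertainty in the arms where one is most needed.

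A second reply is that hospitalisation is a simple proportion while mortality is a Kaplan-Meier rate with censoring, so different methods may be deliberate. An exact interval in every arm also goes beyond the zero-death problem. It drops survivors lost before Day 29 from the denominator while every known death counts, which pushes the proportion slightly upward. That is true. It is small at 5% loss: 1/41 = 2.4% against 1/43 = 2.3%. The narrower repair, exact limits only in zero-death arms, would still leave the negative lower limit at one death under the untransformed form, or coverage down to 82% under log-log.

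Finally, the consequence is limited. No decision rule uses this interval, and deaths are also summarised in the safety analysis (SAP 6.5.2, including "patients with any TEAE leading to death"). A reader can work out the limit from 0 of 43. This limits the importance of the point but does not remove it.

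**Conclusion.** The concern holds. The zero standard error and the exact limits of 6.7% (0 of 43) and 7.0% (0 of 41) follow from the SAP's own method and arm sizes. How often the problem occurs, and the coverage figures, rest on assumed mortality rates and complete follow-up to Day 29. At rates of 2% or below, at least one of the four arms is likely to have no deaths (89% or more). The importance is low: it concerns the error bars of one descriptive secondary endpoint and does not touch the MCPMod primary analysis.

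**What to change.** In SAP 6.4.2:

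1. Keep the Kaplan-Meier Day 29 estimate in the ITT set.
2. In every arm, report a Clopper-Pearson 90% interval for deaths by Day 29 among patients with known Day 29 vital status, and state that denominator.
3. If censoring before Day 29 is material, add a log-log Greenwood interval for arms with at least one death, as a supplement only.
4. Report this at the final analysis. SAP 7 says: "A primary analysis of efficacy and safety is planned after all patients have finished Day 8 visit or discontinued the study earlier". It does not say that Day 29 mortality will be shown at that cut. If it is, take deaths and denominator only from patients randomized at least 28 days before the cutoff, since "Study day is calculated in reference to the date of randomization". Otherwise early deaths count while survivors who have not reached Day 29 leave the denominator.

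**Cost.** Two or three sentences and no new data. The exact interval is conservative (95.0% to 99.9% coverage for a nominal 90%, at 43 patients with no censoring). It does not use the follow-up of patients censored before Day 29, and its proportion can differ slightly from the Kaplan-Meier estimate.

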Kaplan-Meier method will be used to assess the time to resolution of all COVID-19-related symptoms. The corresponding quartiles (including the median) will be reported and a two-sided 95% CI of median, if estimable, will be constructed with a generalized Brookmeyer and Crowley method for each dosing group. Patients who have died prior to experiencing the event of interest will be censored. Their follow-up length will be arbitrarily set as (data cutoff date – first-patient-in date). This approach is to count death as the worst possible outcome without possibility of recovery.

Kaplan-Meier method will be used to assess all-cause mortalities and corresponding quartiles (including the median) will be reported. A two-sided 95% CI of median, if estimable, will be constructed with a generalized Brookmeyer and Crowley method. Patients who does not die will be censored on the last known date alive.

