10.9. Missing Data Handling and Censoring Rules

In general, values for missing data will not be imputed, unless methods for handling missing data are specified.

For MMRM analysis, no imputation will be performed for missing viral shedding. If a patient misses a visit, the missing data will not be imputed. The mixed effect model will handle missing data based on a likelihood method under the "missing at random" assumption.

Sensitivity analyses using method of last observation carry forward (LOCF) may be considered to assess the potential impact from missing data, which will be detailed in the statistical analysis plan (SAP).

Missing dates or partially missing dates will be imputed conservatively for adverse events and prior/concomitant medications/procedures. Specific rules for handling of missing or partially missing dates for adverse events and prior/concomitant medications/procedures will be provided in the statistical analysis plan (SAP).

Censoring rules for analyses of time-to-event endpoints are determined as in Table 5.

Table 5: Censoring Rules for Analysis of Time-to-event Endpoints

No.	Situation	Date of Event or Censoring	Outcome
1	Target event documented	Date of occurrence of target event	Event
2	Multiple target events documented	Date of first occurrence of target event	Event
3	No target event or death occurred by the time of the End-of-Study Visit or the Safety Follow-up Visit (whichever is later), or data cut-off, or withdrawal from study, whichever comes first	Date of last adequate event assessment prior to or on the date of the End-of-Study Visit or the Safety Follow-up Visit (whichever is later), or data cut-off, or withdrawal from study, whichever comes first	Censored
4	Death and no target event prior to death	Date of data cutoff	Censored

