6.2.3 Handling of Missing Data

In general, values for missing data will not be imputed, unless methods for handling missing data are specified.

For MMRM analysis, no imputation will be performed for missing viral shredding. If a patient misses a visit, the missing data will not be imputed. The mixed effect model will handle missing data based on a likelihood method under the "missing at random" assumption.

Sensitivity analyses using method of last observation carry forward (LOCF) may be considered to assess the potential impact from missing data for MMRM in primary analysis.

Missing dates or partially missing dates will be imputed conservatively for adverse events and prior/concomitant medications/procedures. Specific rules for handling of missing or partially missing dates for adverse events and prior/concomitant medications/procedures are provided in Appendix 10.1.

By-visit endpoints will be analyzed using observed data, unless otherwise specified. For observed data analyses, missing data will not be imputed and only the observed records will be included.

Censoring rules for analyses of time-to-event endpoints are determined as in [Table 1](#).

Table 1 Censoring Rules for Analyses of Time-to-event Endpoints

No.	Situation	Date of Event or Censoring	Outcome
1	Target event documented	Date of occurrence of target event	Event
2	Multiple target events documented	Date of first occurrence of target event	Event
3	No target event or death occurred by the time of the End-of-Study Visit or data cut-off, whichever comes first	Date of the End-of-Study Visit or data cut-off, whichever comes first	Censored
4	Death and no target event prior to death	Date of data cutoff	Censored

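### The SAP changes the protocol's censoring dates for symptom resolution and mortality without declaring it, and its censoring table conflicts with its own RT-qPCR rule

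*SAP*

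**What the plan says.** **Protocol.** Table 5 in Section 10.9, row 3, dates censoring for patients with neither target event nor death. The anchor is the "Date of last adequate event assessment prior to or on the date of the End-of-Study Visit". The row then lists further bounds on that date: "Safety Follow-up Visit (whichever is later), or data cut-off, or withdrawal from study, whichever comes first". For mortality, Section 10.2.2 has its own sentence: "Patients who does not die will be censored on the last known date alive". The protocol does not say which of the two governs mortality.

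**SAP.** Table 1 in Section 6.2.3, row 3, reads: "Date of the End-of-Study Visit or data cut-off, whichever comes first". The last adequate assessment, withdrawal and the Safety Follow-up Visit no longer appear. Section 6.4.2 repeats the new rule for mortality ("Patients who do not die will be censored at the time of end of study visit or data cutoff, whichever comes first") and for symptoms ("Patients who have ongoing symptoms will be censored at the time of end of study visit or data cutoff, whichever comes first"). For viral clearance, the same section says that patients who are still positive "will be censored on the last RT-qPCR sample date".

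**Declaration.** Protocol Section 10 requires departures from its planned analysis to be set out in the SAP. SAP Section 8, the place for them, lists none.

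**The concern.** Censoring should stop a patient's follow-up when status is last known. The SAP's dates are visit or cutoff dates, not dates of last knowledge. Three situations that the protocol itself foresees then go wrong.

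1. **Early departure with no End-of-Study Visit.** Protocol 7.4.1 allows for patients who refuse or cannot attend, and 7.4.3 covers loss to follow-up. The visit is due within 7 days of discontinuation (Appendix 1, note c), but the SAP gives no date for a patient who misses it. Only data cutoff is left, so the patient stays at risk with no data.
2. **Early End-of-Study Visit, then seen alive at the Day 31 Safety Follow-up Visit** (Protocol 7.4.2). Known survival between the two visits is dropped.
3. **Primary analysis once all patients have finished Day 8** (SAP Section 7). A patient in follow-up with ongoing symptoms is censored at cutoff, not at the last symptom assessment.

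Cases 1 and 3 can make symptom resolution look slower. For Day 29 mortality, case 1 can lower the estimate and case 2 can raise it. Separately, a programmer cannot follow both Table 1 row 3 and the RT-qPCR sentence.

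**Working it through.** **Inputs.** 43 randomized per arm, 41 with Day 8 data and 5% dropout are from SAP Section 5. The design figure reproduces approximately: 41/0.95 = 43.2, against 43 stated. The documents give no figure for the effect of censoring. I borrow the 5% as early departure: 0.05 × 43 = 2.15, about 2 patients per arm. True median time to resolution (8, 12 or 16 days, exponential), timing of loss and enrolment period are assumptions.

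**Day 29 mortality, one death after the two patients leave.** The estimate is 1/n at risk, with Greenwood SE √[q(1−q)/n].

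| At risk at the death | Estimate | SE |
|---|---|---|
| 43 | 2.33% | 2.30 points |
| 41 | 2.44% | 2.41 points |

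- Case 1: the SAP keeps both at risk (2.33%); last-known-alive does not (2.44%).
- Case 2: the reverse, 2.44% under the SAP and 2.33% under last-known-alive.
- With no deaths, every rule gives 0.

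**Symptom median, case 1, resolution days recorded continuously.** A lost patient adds no events after the loss day L but stays in the denominator:

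F(t) = (1−p)·F0(t) + p·E[F0(min(t, L))], with F0(t) = 1 − e^(−λt), λ = ln 2/median and L uniform.

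Example: true median 12, loss on Days 1–5, p = 2/43. Here λ = 0.05776 and E[F0(L)] = 1 − (e^(−λ) − e^(−5λ))/(4λ) = 0.157. Setting F = 0.5 gives F0 = (0.5 − 0.0465 × 0.157)/0.9535 = 0.5167. So t = −ln(0.4833)/0.05776 = 12.59, a shift of 0.59 days.

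| Patients lost with no visit | Loss window | Shift at true 8 / 12 / 16 (days) |
|---|---|---|
| 2 of 43 | Days 1–5 | 0.31 / 0.59 / 0.87 |
| 2 of 43 | Days 1–29 | 0.05 / 0.13 / 0.24 |
| 1 of 43 | Days 1–5 | 0.15 / 0.28 / 0.42 |
| 1 of 43 | Days 1–29 | 0.03 / 0.06 / 0.12 |

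If resolution is dated at scheduled visits, 10,000 simulated arms per setting leave the median unchanged in 83.6–89.6% (loss Days 1–5) or 95.5–98.2% (Days 1–29).

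**Symptom median, case 3, no dropout.** Enrolment is even over W weeks, so cutoff C is uniform from Day 8 to Day 8 + 7W, with G(c) = P(C > c). Resolution is reported at the next visit and dated back to its true day. Between visits a and b, the hazard under the SAP rule is

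λ·S(t)·G(b) / [G(b)·S(t) + (G(t) − G(b))·S(a)], where S = 1 − F0.

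| True median | W = 4 | W = 8 | W = 12 |
|---|---|---|---|
| 8 | 8.00 | 8.00 | 8.00 |
| 12 | 12.96 | 12.44 | 12.28 |
| 16 | 17.91 | 16.73 | 16.46 |

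The shifts are 0; 0.96, 0.44 and 0.28; and 1.91, 0.73 and 0.46 days. A simulation of 400,000 patients at true 12 gave 12.95, 12.44 and 12.24 under the SAP rule, and 12.00, 12.02 and 11.97 under the protocol rule. If visits and cutoff are counted as elapsed days from randomization (one day less), the shift at true 8 becomes 0.1–0.3 days and the largest shift 2.2 days. If resolution is dated at visits that fall on schedule, case 3 gives no shift.

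**Scale.** The sampling SD of a 43-patient exponential median is about median/(ln 2 × √43): 1.8, 2.6 and 3.5 days at true 8, 12 and 16. Shifts of 0.87 and 1.91 days at true 16 are about 0.25 and 0.54 of that SD.

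**Cross-check.** Simulated 43-patient arms (true median 8 or 14 days, enrolment over 35, 70 or 140 days) gave identical estimates at the final analysis with no dropout. With 5% dropout, the SAP rule moved the median later by 0.03–0.25 days at the final analysis and by 0.05–1.3 days at the Day 8-triggered cutoff. With 20% dropout and no End-of-Study Visit, the shift reached 2.4 days.

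**The case against.** The strongest reply is that this is a consistency edit. The endpoints are descriptive, with no between-arm test. The mortality gap is 0.11 points against an SE above 2 points, most symptom shifts are well inside sampling error, and nothing suggests they would differ by arm. That is right about size, and it is why the correction is minor. It does not make the SAP rule right as written.

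Some specific points stand as limits:

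- **Case 2 depends on the comparator.** Table 5 row 3 also stops at withdrawal, so under it a patient seen later at Day 31 loses that time too and the estimate is again 1/41. The reversal holds only against the last-known-alive sentence.
- **Case 3 rests on the most assumptions:** fast enrolment, a long true median, resolution dated between visits, and the endpoint being reported at the Day 8-triggered analysis. SAP Section 7 names efficacy and safety there but does not list endpoints. SAP 6.2.2 ties time-to-event dates to the actual test date, which may favor visit dating and a near-null effect. SAP 6.4.2 counts "the days from randomization to the first day when all symptoms were resolved", which leaves it open.
- **Case 1 may be rare.** The End-of-Study Visit is required, with telephone contact as fallback, and the 5% was set for missing Day 8 data.
- **The RT-qPCR conflict** would probably be settled in favor of the specific sentence, which agrees with the protocol. The table still says otherwise.

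**Conclusion.** The point holds. The SAP replaces the protocol's censoring dates for symptom resolution and mortality, does not declare the change, and contradicts itself on RT-qPCR. The effect is zero at the final analysis if nobody leaves early.

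With 2 of 43 per arm leaving early, it is about 0.1 percentage point on Day 29 mortality per death and under one day on the symptom median. At the Day 8-triggered analysis the symptom median could move by up to about 2 days, but only with four-week enrolment and a true median near 16 days. These sizes rest on assumed medians, loss times and enrolment periods. The textual mismatch rests on none of them.

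The MMRM and MCPMod primary analysis, its alpha and the sample size are unaffected. This is a minor correction that should be made before database lock. I could not confirm that the protocol text reviewed is amendment 2.0, which SAP Section 1 cites.

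**What to change.** - **SAP Table 1, row 3:** restore the Protocol Table 5 row 3 rule, including withdrawal and the Safety Follow-up Visit as bounds, for time to symptom resolution and time to negative RT-qPCR. State that all-cause mortality is exempt from this row.
- **SAP 6.4.2:** censor symptom resolution at the last symptom assessment. Censor mortality at the last known date alive, up to data cutoff, so that the Day 31 visit and telephone contacts count. The cutoff bound is an addition; Protocol 10.2.2 states none. Keep the last sample date for RT-qPCR.
- **SAP Section 8:** list any departure that is kept, and record that the last-known-alive sentence in Protocol 10.2.2, not Table 5 row 3, governs mortality.

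The cost is SAP wording and derivation code, using visits and contacts that the protocol already requires. One check is needed: Protocol 7.4.3 places contact attempts in source documents, so confirm that last-contact dates also reach the database.
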